### **3.3.4. Gaps in Knowledge to be Addressed by this Project**

In spite of a number of reports (mostly case reports) on UCD, the mortality rate from these disorders remains uncertain. A mortality rate of up to 50% has been quoted in the literature for patients with neonatal onset UCD [22]. However, we have seen much lower mortality rates among the UCDC longitudinal study cohort (23%-34%) but it is unclear whether this discrepancy reflects a real improvement in the management of UCD during the last two decades or whether there exists an ascertainment bias; an effort is underway in the UCDC to remove survivorship bias and reassess the risk of mortality. Conservative management and liver transplantation are associated with mortality and morbidity, due to hyperammonemia in the former, and peri- and post-surgical complications in the latter. It is, therefore, important that we have information to compare survival as well as other outcomes of the two approaches, taking appropriate account of specific disorders ( a type of UCD) and severity (neonatal or late onset). The second major gap in knowledge is with respect to neurocognitive outcome in patients with UCD. While we have both cross-sectional and longitudinal information about patients with UCD managed conservatively [8, 26], we need more information about patients with UCD who underwent liver transplantation. Our collaboration with SPLIT (Studies of Pediatric Liver Transplantation) will enable us to capture all or most patients with UCD who undergo liver transplantation and thus provide a nonbiased evaluation of their outcomes. The third gap in knowledge is regarding the quality of life in patients with UCD, both those managed conservatively and by liver transplantation. Although being on a restrictive diet contributes to a compliance issue, and has been shown to have a detrimental effect on children's quality of life [27], no comparisons with other treatments have been reported. Last but not least, there is a paucity of evidence

about how patients with UCD, their families, and their providers reach a shared decision on which management strategy to choose, how frequently and by what mechanisms these decisions are revisited, and what clinical, social, and/or system level factors influence this decision process. To date, there have been no published studies that examine the experience of providers or patients with UCD and their families in making this critical and difficult treatment decision.

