## 6.2. Analysis Plan

For **Aim 1**, we will use covariate balancing propensity scoring based on the CBPS package in R [28] to create comparable (balanced) groups based on their risk factor (covariate) profile in subjects according to their propensity (probability) to move from conservative management to liver transplantation. This approach leads to a model that predicts treatment assignment (conservative vs. liver transplantation) and balances covariates, especially those related to study outcome(s), and offers the best opportunity to simulate RCT results from observational data. From prior experience, many through the UCDC [26,31,32], we know many of the important risk factors, which include neonatal vs. late onset, number of prior hyperammonemic events, event severity in terms of hyperammonemic coma score [2], ammonia and glutamine levels at regularly scheduled clinic visits, and duration from birth to transplant or index date. In addition to these, we will consider comorbidities, organ function, and other laboratory assessments. The CBPS software will help us choose the model that maximizes covariate balance and generate the CBPS for each participant. The next steps will be to order the dataset according to the CBPS. It is useful at this point to select CBPS to cut points to form homogeneous strata to assess the number of subjects with a liver transplant and conservative management per stratum. Those strata where there are

insufficient numbers (mismatches) of conservative treatment or liver transplant subjects will be described, documented and excluded from the primary analysis due to lack of covariate balance. Before conducting model-based analyses for **Aim 1**, we will compare survival times based on the log-rank test in Kaplan-Meier analysis and the difference between mean scores based on t-tests by treatment for neurodevelopment and quality of life within each stratum to evaluate evidence of heterogeneity. Evidence of heterogeneity will provide clues to interactive effects based on UCD severity which will be modeled in regression analyses below by including a cross products term of treatment type with CBPS. Based on these results, we will develop general linear random effects longitudinal regression models in STATA 14

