[<http://www.stata.com/stata14/>] to perform analysis of covariance that will enable us to evaluate **Aim 1** outcomes of neurodevelopment and quality of life. Each model will include treatment type, the baseline measurement of each outcome, as well as the CBPS and if necessary the cross product of treatment type by CBPS. When we address survival, we will implement Cox Regression models to predict survival time by treatment and will either control for CBPS or stratify on it in the case of heterogeneity.

We used PASS 12 [33] to evaluate statistical power to address study aims for sample sizes per group (liver transplantation vs. conservative management) of 90 and 80 in 2-tailed testing at an alpha of 0.05, which assumes some losses in the sample entering analysis in order to maintain adequate covariate balance between groups. For neurodevelopmental and quality of life assessments, we have 80% power to detect modest 0.4sd effect size differences between groups assuming two repeated measurements per person correlated at 70% (ICC). For mortality, assuming the rate in the conservatively treated group remains about 28%, the study will have 80% power to detect and increase in the liver transplant group of about 60% which is robust to differences in sample size between 80 and 90 per group. The study is well powered to detect any clinically meaningful difference in neurocognitive outcomes and QOL and adequately powered to detect a moderate difference in mortality between groups.

For **Aim 2**, interview data will be managed using QSR International NVivo 10 software [[http://www.qsrinternational.com/products\\_nvivo.asp](http://www.qsrinternational.com/products_nvivo.asp)], a program that allows us to collect, organize, and code qualitative data sources. Although not explicitly a grounded theory study, our approach to the analysis of primary caretaker and provider interview data will borrow from aspects of Strauss and Corbin's systematic procedures for grounded theory work [34]. No existing framework or theory currently exists that describes the process which UCD patients and their families undertake when making the difficult decision to pursue liver transplant or continue conservative management. Thus, some of Strauss and Corbin's analysis techniques are suitable for this study aim, which seeks to describe a process/experience in a field where there is little pre-existing evidence.

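### The treatment x CBPS term planned for effect differences by UCD severity is an interaction with the probability of transplant, and cannot be read as an interaction with severity

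*Combined protocol and SAP*

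**What the plan says.** Section 6.2 (Analysis Plan, Aim 1) first compares the treatments within CBPS strata and then says: "Evidence of heterogeneity will provide clues to interactive effects based on UCD severity which will be modeled in regression analyses below". The term named for this purpose is the product of treatment and the score.

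The same section describes the score as grouping children "according to their propensity (probability) to move from conservative management to liver transplantation". The risk factors it lists are those "which include neonatal vs. late onset, number of prior hyperammonemic events, event severity in terms of hyperammonemic coma score", then ammonia and glutamine at routine visits, and "duration from birth to transplant or index date". Comorbid conditions, organ function and further laboratory values may be added. UCD type is not named, but the list is open-ended.

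The regression models for neurodevelopment and quality of life contain treatment, the baseline value, "as well as the CBPS and if necessary the cross product of treatment type by CBPS". Nothing is said about centring the score or about the score value at which the treatment effect is read. For survival, the Cox model adjusts for CBPS or stratifies on it and has no product term.

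Section 3.3.4 sets the aim of comparing outcomes "taking appropriate account of specific disorders ( a type of UCD) and severity (neonatal or late onset"), which treats disorder type and severity as two separate factors.

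**The concern.** The plan attaches a clinical label, severity, to a variable that measures something else. A propensity score ranks children by how likely they were to be transplanted. Severity contributes to that ranking, but so does anything else that drives the decision. A significant treatment x CBPS term says that the effect changes along this composite. It does not say which component is responsible. Section 6.2 offers no direct interaction with disorder or severity alongside it, so the two factors separated in Section 3.3.4 are never separated in the analysis.

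The study is meant to inform families choosing between the treatments. A difference labelled as severity that came from timing or disorder type would be wrong information for that choice, and a real difference could be missed if components of the score act in opposite directions.

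A second, smaller matter is the parameterisation. Once a product term is in the model, the coefficient on treatment is the effect where the score equals zero. If the score is left on its 0-1 scale, that point lies outside the children analysed.

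**Working it through.** **1. The plan's own figure.** The nearest stated figure is 80% power for a 0.4 SD difference (90 and 80 children, two-sided alpha 0.05, two measurements, ICC 0.7). The SD of the mean of two measurements is sqrt((1 + 0.7)/2) = 0.922. The SE is 0.922 x sqrt(1/90 + 1/80) = 0.142. Power is Phi(0.4/0.142 - 1.96) = 80.6%, so the figure is reproduced. It concerns the main treatment effect; no power is given for any interaction.

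**2. Does UCD type predict transplant?** From Table 2 (transplanted/all):

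- CPSD 12/13 = 92%, OTCD 44/65 = 68%, ASD 22/59 = 37%, ALD 14/48 = 29% (chi-square 29.6, 3 df).
- CPSD + OTCD 56/78 = 72%; ASD + ALD 36/107 = 34%. Odds ratio (56 x 71)/(22 x 36) = 5.0.
- For comparison, peak ammonia above 200: 90/159 = 57%; otherwise 2/26 = 8%. Odds ratio (90 x 24)/(69 x 2) = 15.7.

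Both type and severity predict transplant, so the meaning of the score depends on which covariates are chosen.

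**3. What the product term detects.** The simulations below use 92 v 93 children, a logistic score in place of the CBPS package, and residual SD 0.922. Severity, and timing where used, is shifted 0.6 SD between groups. All of these settings except the group sizes are assumptions.

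*Score from severity and timing only* (effect slope 0.3-0.5 SD per SD). Share of runs significant:

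| True source of effect difference | treatment x CBPS | direct treatment x severity |
|---|---|---|
| Timing only | 32-66% | 4-6% |
| Severity only | 32-66% | 60-95% |
| Severity and timing, opposite directions | 8-11% | 59-95% |

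The product responds equally to timing and to severity, so it cannot tell them apart. It is also weaker than the direct term when severity is the true source. A further run with the baseline outcome in the model gave 26-38% v 5-6% for timing only, and 29-44% v about 76% for severity only.

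*Score with and without UCD type* (Table 2 type counts, 0.8 SD effect difference between CPSD/OTCD and ASD/ALD):

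- Type in the score: correlation 0.83 with type and 0.62 with severity. A purely type-driven difference is significant in 64% of runs (40% in the run with baseline). When type and severity act in opposite directions, it is 9%.
- Type left out: correlation with type 0.11. A type-driven difference is significant in 6% of runs, which is chance level.

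**4. The treatment coefficient with an uncentred product.** In y = b0 + b1 T + b2 S + b3 T x S, the effect at score s is b1 + b3 s. Its variance is sigma^2 x [1/92 + 1/93 + (s - mean_T)^2/SS_T + (s - mean_C)^2/SS_C]. As an illustration, set S to the Table 2 transplant share by type. Then mean_T = 0.578, mean_C = 0.418, SS_T = 3.93, SS_C = 2.28, the overall mean is 0.497 and the lowest score is 0.29.

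- At s = 0: sqrt(0.0216 + 0.0848 + 0.0765) = 0.428. Times 0.922 gives SE 0.394.
- At s = 0.497: sqrt(0.0216 + 0.0016 + 0.0028) = 0.161. Times 0.922 gives SE 0.149.
- Ratio 2.65. Power for 0.4 SD: Phi(0.4/0.394 - 1.96) = 17% uncentred; Phi(0.4/0.149 - 1.96) = 77% centred.

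Across the simulations the ratio ran from 2.2 to 3.8, and the lowest score averaged about 0.10-0.16. With a true average effect of +0.4 SD that rose with severity, the coefficient at zero averaged -0.18 with type in the score and -1.10 with type left out.

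**The case against.** Most of the named covariates are severity items, so the score will usually rise with severity, and Section 6.2 speaks only of clues. If the final score contained nothing but severity, the product would be a fair severity interaction. That limits the charge to mislabelling a composite; it would be wrong to infer that the score is unrelated to severity. The label still fails, because the section itself puts a timing variable in the score.

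A reader might infer that the term does mix disorder type with severity. The documents do not support this as fact: type is not a named covariate. The 64% and 40% figures apply only if it is added.

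The simulations also simplify the plan. Section 6.2 drops strata short of either treatment. With type in the score, dropping quintiles with fewer than 8 children per arm (an assumed rule) cut one type-driven rate from 43% to 24%. The problem shrinks but remains.

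A reader might also infer that the coefficient at zero will be the headline result, or that the survival analysis is affected. Neither is stated. The product enters only if needed, and the Cox model does not use it. Centring leaves the fitted model unchanged, so this part is a matter of parameterisation and reporting. The 17% and 77% above are powers for two different quantities, the effect at zero and the effect at the mean score.

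**Conclusion.** The concern holds in a limited form. For neurodevelopment and quality of life, a treatment x CBPS term cannot be interpreted as an interaction with UCD severity. It may reflect timing, or UCD type if type is put in the score; if type is left out, it will largely miss type-driven differences. This follows from the plan's own definition of the score and needs no simulation. The simulated rates show that the mislabelling can be material, but they rest on the assumed group shifts, effect slopes and logistic score, and are not forecasts for this study.

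The score-of-zero issue is real only if the product is fitted uncentred and the treatment coefficient is then reported alone. In that case the standard error is mostly two to three times the centred one (2.65 in the Table 2 illustration). The documents do not support the further reading that families will be given a false severity message; they show only that the planned term could not justify one. The point should be corrected before analysis, because a better-targeted method is available from data already collected.

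**What to change.** In Section 6.2:

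- State whether UCD type enters the score.
- Test heterogeneity with treatment x one prespecified severity marker and treatment x UCD type, and stop describing treatment x CBPS as severity. The marker could be onset, as in Section 3.3.4, or peak ammonia. Table 2 shows onset of 1-21 days in both groups, so if those figures are ranges a neonatal/late split would hardly vary and peak ammonia is more usable. For type, Table 2 has only one conservatively managed CPSD child, so some grouping is needed; the plan does not prescribe one, and it should be fixed in advance.
- Keep CBPS for adjustment. If its product with treatment is retained, centre the score and report the treatment effect averaged over the children kept after stratum exclusion.

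The cost is a change of analysis wording, with no new data. The downside is one or two more interaction terms in at most 185 children, each with limited power, so they should be reported as exploratory, with confidence intervals.

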## 4.3. Recruitment of Participants

**Aim 1:** De-identified data from the Longitudinal (natural history) Study (LS) of the Urea Cycle Disorders (UCD) will be supplemented with data from subjects identified from two sources: the Studies of Pediatric Liver Transplantation (SPLIT) Research Group and the National Urea Cycle Disorders Foundation (NUCDF).

Longitudinal Study participants will not be recruited to participate in this study, but their data used for this analysis, as is permissible per the LS consent form.

By agreement, when this project is implemented, SPLIT will contact its respective transplant centers to describe the study and its eligibility criteria indicating the number and descriptive characteristics of eligibility based on SPLIT anonymized records asking study staff to contact eligible patients and provide general recruitment materials. NUCDF will also distribute recruitment materials and directly enroll eligible participants to the study. In all cases, interested patients will contact one of the study sites to express their interest in participating in the study.

Enrollment in the UCDC LS will be offered to any patient not already enrolled, so that they can take advantage of the rare disease protocol to capture laboratory data, neurocognitive function and quality of life information, using the resources already in place through the UCDC. Participants interested in enrolling in the LS will be put in

touch with the study coordinator and PI at the nearest (or preferred) UCDC site. The PCORI site coordinator will work closely with LS coordinators to ensure that contact with interested participants is not delayed. We anticipate that a large proportion will agree to participate in the PCORI study, which will require only two visits for neuropsychological testing and self-reported quality of life questionnaire.

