#### **4.5. Data Elements and Schedule of Events**

##### **Aim 1:**

###### **Baseline Visit**

Confirmation of Eligibility: Once enrolled into the study, the participant's diagnostic testing will be reviewed to assure that the correct UCD diagnosis has been made and eligibility requirements are met based on study inclusion and exclusion criteria.

Baseline Assessment: Historical and new data will be collected at baseline as summarized below. We will use a variety of methods to obtain these data. Certain information will be obtained from a historical review of existing charts and laboratory /treatment data. Careful attention will be paid to accurately note dates for historical information. Other data will be obtained from patients or their families through a standard interview. A Quality of Life survey will also be administered at the baseline visit or afterward by phone or through the RDCRN database. Neuropsychological testing will be performed at the same visit, or at another date.

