###### **Historical Data:**

- Eligibility
- Enrollment/demographic information
- Review of past medical records, including:
  - growth charts
  - neurodevelopmental testing
  - neurological evaluation
  - biochemical and diagnostic testing (e.g., ammonia, plasma amino acids, DNA sequencing of UCD genes)

- history of hospitalizations
- medications and other treatments (e.g., dialysis)
- other comorbidities

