**Neuropsychological testing and Quality of life questionnaires:**

Neuropsychological tests will be based on age-matched norms for the specific test used (Table 1). These tests overlap with those currently used in the UCDC LS. The findings will be discussed with the participant/parents at the time of the testing, and a report of the results of this testing will be provided to the participant/parent.

Table 1. Validated tests and scales to be used in this study						
Test	Domain	6-35 mo.	3-5 y	6-16 y	≥17 y	Reference
Bayley-II/III	Overall Development (IQ/DQ)	X				[36]
WPPSI-IV			X			[37]
WASI/WASI-II				X	X	[38]
ABAS-II	Adaptive Skills	X	X	X	X	[39]
CBCL	Mood and Behavior		X	X		[40]
BRIEF	Attention/Executive Skills		X	X	X	[41]
TEA-Ch				X		[42]
RCFT				X	X	[43]
TOL-Dx				X	X	[44]
NEPSY	Attention/Executive, Language		X	X		[45]
D-KEFS				X	X	[46]
WRAVMA	Motor		X			[47]
Grooved Pegboard				X	X	
Grip Strength				X	X	[49]
Beery VMI	Visual Motor		X	X		[50]
CVLT-C/II	Learning and Memory		X	X	X	[51]
PedsQL	Quality of Life	X	X	X		[52]
SF-36				X	X	[53]
PROMISE					X	[54-56]

The Quality of Life questionnaires will be administered at the baseline visit to assess the impact the disorder has on the participant's quality of life. Parents of participants aged 1 month to 18 years old will be administered the PedsQL parent-report or parent proxy-report questionnaire. Participants between 13 and 18 years of age will complete the PedsQL child questionnaires for their age group. Adult participants (over 18 years of age) will respond to the SF-36v2 questionnaire and the Patient Reported Outcomes Measurement Information System (PROMIS) questionnaires annually (43, 44). PROMIS questionnaires: Satisfaction with Social Roles and Activities, Cognitive Function (previously called Executive Function), Anxiety, Depression, Emotional/Behavioral Dyscontrol. The site neuropsychologist and/or the site PI will review PROMIS questionnaires within 30 days of administration and follow up with the participant and his/her family, as appropriate, such as if there is any indication that the participant may harm himself/herself or others

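### The baseline score adjusted for in the neurodevelopment and quality-of-life models is not tied to transplant, so for children first assessed after surgery it can be a post-treatment score that biases the treatment effect

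*Combined protocol and SAP*

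**What the plan says.** Section 6.2 plans random-effects longitudinal regressions for neurodevelopment and QoL. On covariates it states: "Each model will include treatment type, the baseline measurement of each outcome, as well as the CBPS". It gives no timing for the baseline score. The only anchor to surgery in that section is a propensity covariate, age at transplant or index date, and no rule assigns an index date to a conservatively managed child.

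Section 4.5 uses the word baseline for a visit after enrolment. On QoL it says "A Quality of Life survey will also be administered at the baseline visit or afterward by phone" and, later, "The Quality of Life questionnaires will be administered at the baseline visit". Older material comes from a chart review, introduced by "Review of past medical records, including". That list names neurodevelopmental testing but not QoL. On dating, the plan says "Careful attention will be paid to accurately note dates for historical information".

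On who enters, Section 4.3 says "SPLIT will contact its respective transplant centers to describe the study and its eligibility criteria", and that newly enrolled children need two testing visits. For children already followed, it says "Longitudinal Study participants will not be recruited to participate in this study, but their data used for this analysis". Section 4 adds that the Longitudinal Study records neurocognition and QoL. Table 2 in Section 6.1 lists 92 eligible transplanted cases with surgery age 11.7 (1.5-186) months; the statistic is not labelled. Table 1 starts developmental testing at 6 months.

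The power statement in Section 6.2 claims 80% for a 0.4 SD difference with 80 to 90 children per group and two measurements correlated at 0.7.

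**The concern.** Adjusting for a pre-treatment score sharpens a comparison. Adjusting for a score taken after treatment removes whatever part of the effect was already present when that score was taken. A child enrolled through a transplant centre after surgery, with no earlier test on record, has only post-surgical scores. If the first of these is used as the baseline, the model compares change after surgery, not the consequence of having had it.

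The plan does not rule this out, and its operational description of baseline points towards it for newly enrolled children. Two analysts could follow Section 6.2 with different baselines and get different answers. The study is meant to inform families choosing between the two treatments, so a lasting cognitive or QoL benefit or harm that is partly adjusted away would mislead the people it is written for.

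**Working it through.** **Inputs from Section 6.2:** difference 0.4 SD; correlation 0.7; 80 to 90 per group; two-sided alpha 0.05. **Not in the documents:** f, the share of transplanted children whose baseline score follows surgery. It is shown from 0 to 1.

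**The plan's own figure.** The mean of two scores has variance (1 + 0.7)/2 = 0.85. A two-sample comparison of 0.4 SD then has 78% power at 80 per group and 83% at 90, so the stated 80% reproduces. It reproduces without baseline adjustment. With a true pre-treatment baseline and one follow-up score, the residual variance is 1 - 0.7^2 = 0.51 and power is 94-96%.

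**Expected estimate.** The adjusted treatment coefficient is the difference in mean follow-up minus 0.7 times the difference in mean baseline. If a fraction g of the final effect is present in a post-surgical baseline, the baseline difference is 0.4 x g x f, so

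estimate = 0.4 x (1 - 0.7 x g x f).

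**Constant lasting effect (g = 1), one follow-up score.** Power and coverage of the true 0.4 SD come from simulating the baseline-adjusted regression. The simulation has no propensity term and arms that are otherwise balanced.

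| f | Estimate (SD) | Power | 95% CI coverage |
|---|---|---|---|
| 0 | 0.40 | 94-96% | 95% |
| 0.25 | 0.33 | 82-87% | 90-91% |
| 0.5 | 0.26 | 62-68% | 76-78% |
| 0.75 | 0.19 | 38-42% | 53-57% |
| 1 | 0.12 | 18-20% | 28-33% |

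**Two follow-up scores, g = 1, f = 0.5.** The estimate is still 0.26 SD. Power rises to about 77-82%, but coverage falls to about 67-71%, because the interval narrows around the same biased value. A child seen only at the two study visits contributes one follow-up score once the first visit is used as baseline.

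**Other effect shapes:**
- Half the effect present at baseline (g = 0.5): 0.4 x (1 - 0.35f), which is 0.33 SD at f = 0.5 and 0.26 SD at f = 1. The loss is halved.
- An early dip of half the effect (g = -0.5): 0.4 x (1 + 0.35f), which is 0.47 SD at f = 0.5. The estimate is inflated.

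**Other correlations, g = 1, f = 0.5:** 0.4 x (1 - 0.5 x 0.5) = 0.30 SD at a correlation of 0.5, and 0.4 x (1 - 0.8 x 0.5) = 0.24 SD at 0.8.

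**The case against.** The strongest reply is that this is an unstated definition, not a planned error. Section 6.2 speaks of the propensity to move from conservative management to transplant and of approximating a randomized trial, which suggests a pre-treatment baseline. Longitudinal Study data enter directly and include both cognition and QoL, and dated historical developmental tests are collected for newly enrolled children. Much of this stands. It means f may be small for cognition, and for QoL too among children followed in the Longitudinal Study before surgery. A reader might infer that QoL has no pre-transplant source for anyone because the chart-review list omits it. The documents do not support that; the gap is confined mainly to children outside the Longitudinal Study. Nor does the remark in Section 3.3.4 that "we need more information about patients with UCD who underwent liver transplantation" show that pre-transplant scores are missing, since it concerns outcomes after transplant.

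The reply does not close the point. Section 6.2 never names these earlier scores as the baseline, and children first reached after surgery may have none.

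A second objection is that dropping baseline adjustment for everyone could be worse. This also stands. If transplanted children differ by d before the index date after propensity adjustment, the unadjusted error is d and the planned model's error is 0.3d - 0.28f (g = 1). For d = -0.1 SD, dropping the baseline gives the smaller error only if 0.03 + 0.28f exceeds 0.10, that is f above 0.25. For d = +0.1 SD it requires 0.28f - 0.03 above 0.10, that is f above about 0.46. At d of 0.2 SD in size the thresholds are 0.50 and 0.93. Table 2 shows median peak ammonia of 958 against 403, and Section 3.3.2 links status after transplant to status before it, so residual differences are a real worry.

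**Conclusion.** The point holds in conditional form and should be fixed. As written, Section 6.2 allows a post-transplant score to serve as the baseline covariate, and for children first assessed after surgery with no earlier score it would bias the treatment effect. The size depends on f, which the documents do not give. Under the plan's 0.4 SD and 0.7 correlation with a constant effect, 17.5% of the effect is lost at f = 0.25 (0.7 x 0.25), 35% at f = 0.5 and 70% at f = 1. These are scenarios, not predictions.

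Three stronger readings are tempting and are not supported:
- That most transplanted children will have a post-surgical baseline: no count is given.
- That the bias always runs towards no difference: it does when the baseline shift shares the sign of the final effect and is not too large, but Section 3.3.4 mentions complications around and after surgery, and an early dip would inflate a benefit.
- That the stated 80% power is wrong: it is correct for the mean of two scores and conservative for a true pre-treatment baseline. It simply does not describe the planned model when f is large.

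**What to change.** In Section 6.2:

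1. Define the outcome baseline as the last score before transplant or, for controls, before an index date. Assign the index date by a stated rule before the propensity score is fitted, because time to index date is one of its covariates. One option is to draw it from the transplant ages of children with the same disorder and onset group, restricted to ages at which the control was alive and untransplanted.
2. State that a post-transplant score is never used as the baseline covariate and is analysed as an outcome.
3. Keep baseline adjustment where a pre-index score exists. For children without one, rely on the propensity score and pre-index covariates. The sponsor should name in advance either the baseline-adjusted subset or the all-children model as primary, and report the other as a sensitivity analysis.
4. Report, per arm and per outcome, how many children have a pre-index score.
5. Restate power for the model chosen, allowing for the propensity term. For illustration, an unadjusted comparison has 71-76% power with one score per child and 78-83% with two. If the propensity score explained 20% of the variance in treatment (an assumption, ignoring any offsetting gain in outcome precision), these would fall to 61-67% and 68-74%.

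No new data are needed: the cost is wording, an index-date rule and a new power statement. The drawback is some loss of precision and heavier reliance on the propensity score to control confounding in children without a pre-index score. That group may be large. Surgery age is given as 11.7 (1.5-186) months and developmental testing starts at 6 months, so a child transplanted near the lower end could not have an earlier Table 1 developmental score, and controls given similarly early index dates would have the same gap.
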